## 11 ETHICAL CONSIDERATIONS

The sponsor of the study is Laboratorios Andrómaco S.A.

According to the established in Chile, recruitment of patients for this type of studies is governed by Act 20120. Before any procedure or intervention takes place, the informed consent form must be signed.

According to scientific evidence currently available, this study is classified as a “minimum risk” study for the patients and their unborn children.

## 12 PROTOCOL AMENDMENTS

Any substantial amendment to this protocol requires approval from the Independent Ethics Committee prior to its implementation.

## 13 ACCESS TO THE DATABASE/DOCUMENTS

Participating investigators and institutions will have access to controls, audits, reviews, and regulatory inspections by the entities governing the study, and will provide required data and documents safeguarding the identity of the participating patients.

1. INTRODUCTION

This statistical analysis plan is for Andromaco Laboratory S.A., Protocol PCP 002, multicenter, randomized, controlled, open label study to evaluate the efficacy of a vaginal cerclage pessary with a sustained progesterone release, in doses of 6.3 g and 7.7 g for the prevention of premature birth.

The reference materials for this plan include the Clinical Protocol (Version 3, 16 May 2016) and the documents with data specific for the study.

As a background of statistical methods that will be mentioned herein, this sections offers a general vision of the study's objectives and design. It is understood that this is only a summary and that the protocol is the final reference for all the matters discussed as follows.

2. OBJECTIVES

PRIMARY

To evaluate the efficacy of two cerclage pessaries containing 6,3 g and 7,7 g of micronized progesterone of sustained release, in the prevention of premature birth, established through spontaneous delivery after 32 weeks but before 34 weeks of gestation, when the pessary is inserted between week 16 and 24, and removed at 36 6/7 weeks of gestation in pregnant women at risk of premature birth.

SPECIFICS

- Record the occurrence of premature rupture of membranes before weeks 32 and 34 weeks of gestation.
- Evaluation of anatomical characteristics of the cervix in pregnant women: position and length.
- Establish the acceptability and tolerance in pregnant women, with the use of the cerclage pessary.
- Evaluation of local and systemic safety in pregnant women, with the use of the cerclage pessary.

3. STUDY DESIGN

A phase II, efficacy, multicenter, controlled, open label, parallel and randomized exploratory clinical study. It will include singleton pregnant subjects, with history of premature birth and/or short neck and an increased risk of premature birth, who, after reading the informed consent, voluntarily accepted to participate in the study.

For the secondary outcomes, subjects will be their own controls on the following variables to assess: anatomical characteristics of the cervix – position and length; development of surveys in pregnant women to establish the acceptability and tolerance of the intervention; and aspects of local and systemic safety.

Two hundred and seventy +10% pregnant women with risk of premature birth will be enrolled at the participating sites. This population will be divided into 3 groups of treatment with 90 participants each, where control group (A) is with intravaginal capsule of micronized progesterone 200 mg, groups B and C are pessaries with 6.3 g and 7.7 g of sustained release progesterone respectively.

In the prenatal and/or ultrasound control between 16 and 24 weeks of gestation, they will be informed and invited to participate in the study. The inclusion of the volunteers will be in all cases until weeks 24 (0/0) of gestation. The volunteers will be selected on the basis of their clinical history and by trans-vaginal ultrasound performed between 16 and 24 weeks. All volunteers with unique pregnancy and cervical length ≤ 25 mm but ≥ 10 mm, will be invited to participate in the study. Prior to inclusion in the study, it is confirmed the vitality of the fetus or other exclusion criteria detailed later. Subjects who refuse to participate in the study will receive the current standard of care in each participating site, according to their condition.

EVALUATION VISITS

The study includes 8 visits to the site. The programmed schedule of assessments for its conduction and the activities to take place in each and one of them are specified in Table 1.

SAMPLE SIZE

The sample size calculation is based on the power to detect differences in the proportion of spontaneous birth between 32 and 34 weeks of gestation, between the formulations of cerclage pessaries with respect to the control group (vaginal progesterone 200 mg capsules). Data collected of at least 90 women in each group will provide at least 80% of the power to detect differences with a rate of 40% or more, using a test of Chi-square of two tails with $\alpha = 0.05$ without correction.

We estimate that up to 10% of the enrolled women may not complete the study, so it must be planned to enroll at least 99 pregnant women in each group to reach at least 198 treated subjects with cerclage pessary and 99 subjects treated with soft capsules of progesterone as a control group (i.e. 99 per each vaginal formulation).

RANDOMIZATION

The randomization will be generated by an independent statistician. The program will be linked in sequential numbers with the code of randomized treatment. A qualified staff member of ANDROMACO laboratory will keep randomization codification, until the database is clean and ready for analysis. The treatment will be dispensed according to the randomization code, the women with unique pregnancy enrolled, will be randomized to receive one of the vaginal formulations of the study.

For the next volunteer, the site will have the next randomization number available. Each woman will receive only the formulation corresponding to the randomization number. The Investigator will record on the log the randomization number and the printed code on each formulation container. Each sites coordinator will assign the randomization code to the volunteers.

Subjects will be randomized to the following three study groups:

- Control Group (A): Intravaginal capsule of micronized progesterone 200 mg on a daily basis.
- Pessary Group (B): Pessary with 6.3 g of sustained release progesterone for a period of around 4 to 5 months.
- Pessary Group (C): Pessary with 7.7 g of sustained release progesterone for a period of around 4 to 5 months.

4. DOCUMENTS AND CHANGE OF VERSIONS

Version #	Date of Review	Date of Approval	Reason for Change
1.0	05Apr2017		N/A
2.0	21Apr2017		Additions to different sections
3.0	12May2017		English Version and clarification of some issues

CHANGES IN THE PLAN

At the moment there are no changes to the protocol or in the conduction of the study.

5. ANALYSIS CONVENTIONS

The statistical analysis will be made by ILS Clinical Research under the authorization of Laboratorio Andromaco S.A.

GENERAL PRINCIPLES

The statistical analysis will be provided to give a general summary of the study subjects and a vision of the efficacy and safety of the results. The data provided by the sites will be summarized for this purpose. Tables of absolute and relative frequencies will be constructed for the quality variables. All the percentages will be presented with a decimal. The quantitative variables will be summarized with the number of subjects participating (n), mean, standard deviation (SD), and median, maximal and minimal.

Two tailed test will be carried out for all the analysis and the type I error is 0.05 for continuous variables and the discrete variables. All p values shall be rounded to three decimal and the values under 0.001 will be presented as <0.001 and values greater than 0.999 will be presented as 1.000. A comparison of the treatment groups will be done with respect to the demographic and baseline characteristics using inferential statistical techniques to detect if any of these variables may condition the results in the dependent variables. Comparisons in qualitative variables will be carried out using the Cochran-Mantel-Haenszel (CMH) test of general association, while the comparisons in quantitative variables will be made with a test of comparison of means (ANOVA analysis of variance) for independent samples with normal distribution. In the cases of no normality on the continuous variables, or in case of not belonging to the exponential family for discrete data, the parametric tests will be replaced for nonparametric tests such as Kruskal-Wallis or Friedman. These tests will be presented in each table as deemed necessary. All confidence intervals will be two-tailed and at 95%.

Table 1: Study Schedule of Assessments

Activities	Visit 1	Visit 2	Visit 3	Visit 4	Visit 5	Visit 6	Visit 7	Final Visit
Demography	X							
Medical History	X							
Physical Exam	X	X	X	X	X	X	X	X
Gynecological Exam	X							
Vital Signs	X	X ¹	X ¹	X ¹	X ¹	X ¹	X ¹	X ¹
Transvaginal Ultrasound	X	X ²	X	X	X	X	X	X
Pre-birth Control	X							
Obstetric Background	X							
Lab Tests (Blood and Urine)	X							
Eligibility	X							
Vaginal Discharge	X	X ³	X ³	X ³	X ³	X ³	X ³	X ³
Randomization	X							
Pessary Insertion	X							
Acceptability and tolerance to the insertion	X							X
Concomitant Medications	X	X	X	X	X	X	X	X
Evaluation of the Pessary's Adhesion (Groups B and C)		X	X	X	X	X	X	X
Treatment Compliance (Group A)		X	X	X	X	X	X	X
Adverse Events	X	X	X	X	X	X	X	X
Subject's Evaluation		X	X	X	X	X	X	X
Birth ⁴								X

1. Pulse and Temperature are added

2. Confirmatory

3. Smear

4. Birth Characteristics: Medication (corticosteroids, antibiotics, tocolysis), hospital admissions; Delivery (Home, Via, interruption); Newborn baby (gender, weight, size, gestational age, head circumference, weight EG, Apgar score); Neonatal complications (infection, respiratory distress syndrome, Intraventricular hemorrhage, Necrotizing Enterocolitis, retinopathy, Blood Transfusion, other); Interventions; Conditions at discharge.

The statistical analysis will be made with SAS software, version 9.2 or greater.

DATABASE MANAGEMENT

The data will be attached to the statistical report. The subjects that will not participate in the analysis (subjects that only completed baseline) will not be included in the tables and figures but they will be included in the listings of data.

6. POPULATION DEFINITIONS

In order to meet the needs of the sub-groups of the Protocol, the following population sub-groups are defined:

Per Protocol (PP): It is defined as the subset of participants who meet the criteria of selection, who expressed their desire to participate in the study, who signed the informed consent form, that the drug has been administered to them and have completed all the visits required or till the termination of the pregnancy as per Protocol.

Intention to treat (ITT): It is defined as the subset of participants who meet the selection criteria, showing their desire to participate in the study, who signed the informed consent form, that the drug has been administered to them, who have at least completed the initial visit and at least one of the subsequent visits to the pessary referred to in the Protocol.

The main efficacy analysis will be carried out with a focus Per Protocol (PP), however it will also be carried out per Intention to Treat (ITT) all the analysis. Otherwise, the main safety analysis will be completed as ITT.

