#### 5.5. Placement and repositioning of the cerclage pessary containing sustained-release progesterone

Once the cervix length and positioning have been examined by transvaginal ultrasound, and any vaginal infection has been ruled out or treated, the progesterone pessary should be implanted by a professional qualified and trained for that purpose. For placement, the participant must be lying in supine position.

The removal of the pessary will be done by vaginal examination at week 36 6/7 or earlier, if there is any medical indication for induction of premature labor or elective cesarean section. The pessary will also be removed from participants in preterm birth labor not responding to treatment with tocolytics.

During controls or visits to emergency departments or medical offices, participants who report vaginal discharge should be examined by a physician to rule out infection by relevant testing (vaginal discharge smears for PCR), and deliver the appropriate treatment without the need to remove the pessary. This condition will be considered an adverse event.

In the event that the medicated cerclage pessary is spontaneously expelled it, will be repositioned within maximum 72 hours; if this does not occur, the patient will be withdrawn from the study but considered in the final statistical analysis under the intention-to-treat principle.

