#### 5.6. Adherence and resuming the treatment in patients assigned to the group treated with vaginal progesterone capsules.

Use of capsules at least during 80% of the exposure time, and resuming the treatment not later than 72 hours after discontinuation for any cause will be considered an acceptable adherence to treatment. If adherence of a patient is below 80% or the treatment is interrupted for more than 72 hours, she will be withdrawn from the study but considered in the final statistical analysis.

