#### 5.7. Study participant withdrawal

The progesterone cerclage pessary will be removed if the patient requests so, or if there is any adverse event not responding to treatment alternatives such as pathological vaginal discharge non-responsive to antibiotic therapy. These participants will not be replaced and the information collected from them will be included in the analysis since this is based on the intention-to-treat principle.

Follow-up of subjects withdrawn from the investigational product will be the same as the standard follow-up.

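### The SAP's ITT set requires a later visit and is also the main safety set, so it drops treated women withdrawn without returning, whom Protocol 5.5 to 5.7 keep in the analysis

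*SAP*

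**What the plan says.** SAP section 6 defines two populations. The set called ITT requires that a woman meets the selection criteria, has consented, has been given the product, and belongs to those "who have at least completed the initial visit and at least one of the subsequent visits to the pessary referred to in the Protocol". The per-protocol set has a different visit condition: its members "have completed all the visits required or till the termination of the pregnancy as per Protocol". The main efficacy analysis is per protocol, with all analyses repeated in the ITT set. For safety, "the main safety analysis will be completed as ITT". No separate safety population is defined, yet section 11.1 divides by the number of women in the safety analysis.

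SAP section 5 (Database Management) adds that women with baseline data only "will not be included in the tables and figures but they will be included in the listings of data".

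The protocol takes a wider view of who is analysed:

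- Section 5.5, pessary expelled and not repositioned within 72 hours: the woman is "withdrawn from the study but considered in the final statistical analysis under the intention-to-treat principle".
- Section 5.6, capsule use under the 80% adherence threshold, where the rule continues: "or the treatment is interrupted for more than 72 hours, she will be withdrawn from the study but considered in the final statistical analysis".
- Section 5.7, pessary removed on request or for an unresponsive adverse event: "the information collected from them will be included in the analysis since this is based on the intention-to-treat principle".

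SAP section 1 says that the protocol governs, and SAP section 4 declares no changes to it.

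**The concern.** A set that requires eligibility, dosing and a return visit is a modified ITT set, and two of those three conditions depend on what happens after randomisation. A woman who starts treatment, stops early and never comes back is kept by the protocol and dropped by the SAP.

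Two uses of the set make this matter. For efficacy, it is the only check on a per-protocol result, and one set filtered after randomisation is a weak check on another. For safety, it supplies the main denominator. The women most likely to leave after one visit may include those for whom insertion went badly, and their events would then be recorded but left out of the main percentages.

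**Working it through.** The point rests on comparing texts, so the check is case by case.

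**1. Who is kept and who is dropped**

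| Woman | Protocol 5.5 to 5.7 | SAP sections 5 and 6 | Result |
|---|---|---|---|
| Treated, withdrawn for expulsion, non-adherence or removal, at least one later visit | Kept | In ITT, if eligible | No conflict |
| Treated, withdrawn for one of these reasons, no later visit | Kept | Not in ITT; outside tables and figures | Direct conflict |
| Treated, no later visit for some other reason | Not addressed | Not in ITT | Departs from the principle only |
| Randomised but ineligible, or never given the product | Not addressed | Not in ITT | Departs from the principle only |
| Delivers before Visit 2 | Not addressed | Depends on whether the birth visit counts as a later visit | Needs a clarifying phrase |

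Only the second row contradicts an explicit rule. The third and fourth depart from the intention-to-treat principle that Protocol 5.5 and 5.7 invoke.

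**2. Whether the second row can occur**

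Protocol 5.5 withdraws a woman if an expelled pessary is not back in place within 72 hours. Under Protocol 5.4.3, controls may be up to 4 weeks apart until 28 weeks. SAP section 9 ends participation when a pessary has to be removed. Withdrawal can therefore come before any scheduled return visit.

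**3. Safety**

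- SAP Table 1 schedules both pessary insertion and adverse event recording at Visit 1.
- SAP section 10 collects ease of insertion, insertion pain and the first VAS at that visit.
- Protocol 8 documents adverse events from consent.
- Protocol 5.7 states: "The progesterone cerclage pessary will be removed if the patient requests so".

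A woman with an event at insertion, removal on request and no return thus has data on file but is outside the main safety set. Such an event could include severe trauma to the vagina or cervix, which SAP 11.1 lists among pessary-attributable complications of interest.

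**4. Denominators in SAP section 11**

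Section 11.1 uses the safety analysis, which section 6 equates with ITT. Section 11.2 defines the crude incidence rate over the whole treatment group, and also plans a summary for everyone enrolled. Section 12 adds all-enrolled listings. The wider bases do not agree with section 6 or with the baseline-only exclusion in section 5.

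**5. Size**

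The related figure in the plan reproduces: Protocol 9.1 needs 90 per group and enrols 99, and 90 × 1.10 = 99. The difference, 99 − 90 = 9 per group, allows for women who do not complete the study. It does not count women without a later visit. Neither document gives that count, or the outcomes of those women, so no bias can be calculated.

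**The case against.** The strongest reply is that the affected group is narrow. SAP section 10 records expulsion and requests for early removal at a Final Visit, which suggests that such women are expected to return once. Capsule compliance is assessed only from Visit 2 (Table 1), from counts at the start of each visit (section 9), so poor adherence is normally found at a later visit, which itself qualifies the woman for ITT. This stands and limits the likely number. It does not help the woman who never returns.

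Safety is also partly covered by the all-enrolled summary, the treatment-group denominator and the listings. That stands too, but the main percentages still rest on the restricted set. The rule that the protocol governs confirms the mismatch without saying which women enter the tables. The study is an exploratory Phase II trial, which lowers the stakes but not the need for one definition.

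Some stronger readings are tempting but not supported:

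- *Every exclusion contradicts the protocol.* Sections 5.5 to 5.7 cover only expulsion, non-adherence and removal.
- *The per-protocol set is not contained in ITT.* Table 1 places birth in the Final Visit column. If that counts as a later visit, which is the natural reading, the problem disappears.
- *Insertion trauma is a named event of interest.* SAP 11.1 names severe vaginal or cervical trauma attributable to the pessary and does not mention insertion.
- *The filter favours the pessary arms.* Capsule users are also withdrawn after a 72-hour interruption, and no uneven loss is shown.
- *The allowance of 9 per group bounds the loss.* Non-completers with one later visit stay in the set, while ineligible completers are removed, so 9 is neither an estimate nor a cap.

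**Conclusion.** The concern holds in limited form and should be fixed. The SAP's ITT is a modified set. It conflicts directly with Protocol 5.5 to 5.7 for women who started treatment, were withdrawn for one of the reasons given there and had no later visit. It departs from the stated principle, though from no explicit rule, for randomised women who were ineligible or untreated. As the main and only defined safety set, it can leave Visit 1 adverse events out of the main percentages, with partial and inconsistent cover elsewhere in the SAP.

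The number of women affected is unknown and may be small, and neither the size nor the direction of any bias can be computed. The conclusion assumes only that some treated women may not return, and that section 6 is applied as written.

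**What to change.** - Define ITT as all randomised women analysed as assigned. Take delivery outcome from hospital records or the treating physician, the sources that Protocol 5.8 already names, whether or not the woman returned.
- Define a safety set of all women who received or began to receive a study product, analysed by treatment received, and use it as the single denominator in SAP section 11. Align the all-enrolled summary in 11.2 with it.
- Delete the baseline-only exclusion in SAP section 5.
- If the present set is kept as a sensitivity analysis, call it modified ITT and state that a birth or early-termination visit counts as a later visit.
- Reconcile SAP section 9 with Protocol 5.5 to 5.7 on follow-up after withdrawal. SAP 9 ends participation at removal, Protocol 5.5 and 5.6 withdraw the woman from the study, and 5.7 continues standard follow-up without saying whether that means study visits.
- Show women with no later visit, by arm, in the planned CONSORT diagram.

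The cost is SAP rewording and retrieval of delivery outcomes for the women who did not return, whose number is unknown.

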7. SUBJECT DISPOSITION

The subjects that were randomized, completed the study PP and the ITT will be summarized in a table indicating the frequency number and percentage. A CONSORT diagram will be included to observe the availability of subjects in the study.

PROTOCOL DISCONTINUATIONS

The number of subjects and their percentage will be included in the table that includes those subjects that were excluded due to lack of compliance to the requested criteria in the protocol. It is important to identify the subjects that did not conclude the study before the definition of populations to study. Discontinuations to the protocol include: Adverse Events leading to discontinuation, failure to meet inclusion/exclusion criteria, failure to comply with the treatment, failure to comply with the visits, concomitant medication, medical contraindication, voluntary withdrawal of the subjects, death, or others.

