9. TREATMENT COMPLIANCE

For Group A, at the start of each visit, it will be recorded the number of capsules dispensed at the previous visit and the number of capsules used, the treatment compliance will be estimated in percentage. The compliance should be between 80 and 120% for each patient.

For groups B and C, it will only be recorded if removal of the pessary was necessary. In this case the subject will be early terminated from the study and the reason for discontinuation will be recorded.

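### The SAP leads efficacy with a per-protocol set although the protocol commits to intention-to-treat, and neither planned set contains all randomised women

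*SAP*

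**What the plan says.** **Protocol.** Section 5.5: a woman whose expelled pessary is not repositioned within 72 hours is withdrawn but analysed by intention-to-treat. Section 5.7: women whose pessary is removed at their request or for an unresolved adverse event are not replaced, and their data stay in because the analysis follows intention-to-treat. Section 5.6: capsule users below 80% adherence, or with a gap over 72 hours, are withdrawn but kept in the final analysis (the term intention-to-treat is not used there).

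**SAP section 6.** "The main efficacy analysis will be carried out with a focus Per Protocol (PP". The per-protocol (PP) set takes eligible, consented, treated women who "have completed all the visits required or till the termination of the pregnancy as per Protocol". The ITT set takes eligible, consented, treated women "who have at least completed the initial visit and at least one of the subsequent visits". All analyses are repeated on ITT, which is the main set for safety only.

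**Other SAP text.**
- Section 5: "The subjects that will not participate in the analysis (subjects that only completed baseline) will not be included in the tables and figures". These women appear only in listings.
- Section 7 counts as discontinuations, among others, "failure to comply with the treatment, failure to comply with the visits, concomitant medication, medical contraindication, voluntary withdrawal of the subjects".
- Section 9, capsules: "The compliance should be between 80 and 120% for each patient".
- Section 9, necessary pessary removal: "In this case the subject will be early terminated from the study and the reason for discontinuation will be recorded".
- Section 1 says that "the protocol is the final reference for all the matters discussed as follows". Section 4 records no departure from the protocol on analysis sets.

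**The concern.** SAP section 10 tests for a difference between each pessary and the capsule, and for superiority of one pessary dose over the other. It is not a non-inferiority test, so PP has no special claim to lead. The dose conclusion depends on the comparability that randomisation provides.

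PP conditions on what happens after randomisation, and the routes out differ by arm: removal or expulsion for the pessary, capsule count for the control. Some routes may be tied to the outcome. Protocol section 5.5 has the pessary removed in preterm labour that does not respond to tocolytics; SAP section 9 treats necessary removal as early termination, and the capsule arm has no counterpart. The trial is open-label, and SAP section 7 has non-completers identified before the populations are defined, so set membership could be judged with treatment known.

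If PP and ITT disagree, the SAP makes PP the leading result. Falling back on ITT does not give the analysis that the protocol promised either.

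**Working it through.** **Step 1. Who is counted, document against document.**

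| Woman | Protocol | SAP PP (main) | SAP ITT |
|---|---|---|---|
| Pessary removed on request or for an adverse event | Counted (5.7) | Early terminated (section 9), so required visits normally missed: out unless the end-of-pregnancy clause keeps her | In, if she has a later visit |
| Pessary expelled, not repositioned in time | Counted (5.5) | Not addressed directly; out if she stops visits | In, if she has a later visit |
| Capsule adherence below 80% or gap over 72 h | Counted (5.6) | Section 7 lists non-compliance as a discontinuation; likely out | In, if she has a later visit |
| Baseline visit only | Not excluded | Out of tables (section 5) | Out |
| Randomised, then found ineligible or never treated | Not excluded | Out | Out |

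Neither SAP set is all randomised women.

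**Step 2. Two ambiguities.** The PP clause on termination of the pregnancy, with protocol section 5.4.5 (a case closes at 36 6/7 weeks or at preterm birth), may keep a woman who delivers after removal in preterm labour. SAP section 9 calls her early terminated, and the two are not reconciled. Also, a woman who delivers before any later visit could be in PP through that clause yet outside ITT, unless the Final Visit counts as a later visit. ITT may then not contain PP.

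**Step 3. The plan's own numbers (protocol 9.1).** 90 × 1.10 = 99 enrolled per group; 99 − 90 = 9 non-completers, and 9/99 = 0.0909. (Dividing gives 90/0.90 = 100, close to 99.) Over three groups, 297 − 270 = 27, or 297 − 3 × 89.1 = 29.7 at exactly 10% loss. About 27 to 30 randomised women could fall outside the main set if non-completion means exclusion from PP.

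**Step 4. Illustration of possible bias.** Assume equal true risk in the arms. Let r be the fraction excluded and m their risk as a multiple of the arm average (1 = pessary, 0 = capsule). Then

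PP risk ratio = [(1 − r1·m1)/(1 − r1)] / [(1 − r0·m0)/(1 − r0)].

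The base risk cancels, but m times base risk cannot exceed 1: m = 2 needs a base risk of at most 50%, m = 2.5 at most 40%, m = 3 at most 33%. All m, and any split of losses between arms, are assumptions; the 9/99 comes from the plan.

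- Pessary arm only, r1 = 0.0909: m = 2 gives 0.8182/0.9091 = 0.90; m = 3 gives 0.7273/0.9091 = 0.80.
- Capsule arm only: 1/0.90 = 1.11 and 1/0.80 = 1.25.
- Same r and m in both arms: 1.00.
- Wider range, pessary arm only: r1 = 0.05, m = 2 gives 0.90/0.95 = 0.95; r1 = 0.15, m = 3 gives 0.55/0.85 = 0.65.
- r1 = 0.10, r0 = 0.15, m = 2.5 in both: 0.8333/0.7353 = 1.13.

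**Step 5. Effect on the test.** With 10% excluded from the pessary arm, none from control, m = 2 and 99 randomised per arm, the risk ratio is 0.80/0.90 = 0.89. By normal approximation the two-sided type I error is then about 0.062, 0.067 and 0.079 at true risks of 15%, 20% and 30%, against a nominal 0.05. With 10% excluded from both arms it stays at 0.05.

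**The case against.** - **ITT is also run, and a CONSORT diagram is planned in an exploratory Phase II trial.** True, and a reader could see PP and ITT diverge. But ITT is a modified set and is ranked second for efficacy.
- **The protocol never formally defines an analysis population.** True. Its intention-to-treat wording is in operational sections, and section 9 counts the 270 as completers. But a sample size based on completers does not define who is analysed, and sections 5.5 to 5.7 say who is counted.
- **SAP section 4 concerns changes to the protocol or its conduct.** Fair. It does not certify that the SAP matches the protocol. What stands is that the departure is not recorded or justified, while section 1 gives the protocol the last word.
- **PP exclusions are inferred.** Partly true. PP has no adherence criterion, the 80–120% range has no stated consequence, and the end-of-pregnancy clause may retain many women with the primary event. This makes the bias uncertain; it does not show that it is absent.
- **The illustration is lightly anchored.** Accepted. One-sided loss is an assumption, 15% exceeds the plan's figure, and non-completion need not equal PP exclusion.
- **The gap between ITT and all randomised may be small**, since eligibility, randomisation and insertion all fall at Visit 1. Possibly, but the documents do not size it.
- **Withdrawal from the study is not the same as stopping the product.** This stands. The follow-up promise in section 5.7 covers the latter, so retrieval of outcomes for the former must be made explicit.

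**Conclusion.** The concern holds. The SAP's main efficacy set contradicts the protocol's intention-to-treat commitment, the change is not justified, and the SAP's ITT set does not restore the full randomised population. This follows from the text and needs no assumption.

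The consequence cannot be sized from the documents. With no true effect and loss at the plan's 10% allowance (9 of 99) in one arm only, at an assumed 2 to 3 times average risk, the PP risk ratio lies between 0.80 and 0.90 or between 1.11 and 1.25, depending on the arm. It is 1.00 if losses match. The bias could favour either treatment. The point should be settled before the data are analysed.

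**What to change.** 1. **SAP section 6:** make the main efficacy analysis all randomised women in their assigned group, whatever their adherence, removal, expulsion or number of visits. Keep PP as supportive. Rename the current ITT set modified ITT and keep it as supportive too.
2. **SAP sections 5 and 9:** state that early-terminated, withdrawn and baseline-only women in all three arms remain in the main analysis.
3. **Outcome retrieval:** state that gestational age and type of delivery are obtained for every withdrawn woman from hospital records or the treating physician, the source already named in protocol section 5.8.
4. **Missing outcomes:** fix in advance how women with no retrievable outcome enter the comparison of proportions, report their number by arm, and add a sensitivity analysis over the possible outcomes.
5. **PP wording:** say whether women who deliver after pessary removal belong to PP, and whether the Final Visit counts as a later visit.
6. Reconcile SAP sections 6, 7 and 9 with protocol sections 5.5 to 5.7 on the analysis set only. No change to any removal, repositioning or stopping rule is implied.

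**Cost:** SAP wording, one analysis not now planned, and tracing outcomes for early withdrawals. The estimate may be somewhat diluted by non-adherence. Recruitment is unchanged at 99 per group.
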